### 13.2. Criteria for Termination of the Trial

The trial will be terminated upon completion of the final study visit by the last participant or unless any of the conditions of Section 7.4 are met. An active participant is one who is enrolled in the study and has not been discontinued.

### 13.3. Accountability of Data

Individual data points that are missing will be excluded from analysis involving only those specific variables. A participant's complete visit data will not be excluded if some of the observations are missing. Inclusion of outliers in the analysis will be based on the magnitude of change in test statistic with and without the outliers. Outliers will preferably be retained unless there is significant change in test results.

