### 6.1.3. Clinical Trial Population

A total of 46 participants with dry eye disease will be required to complete the study.

Trial participants will be recruited from the local population at the investigational site. An e-mail invitation will be circulated to [REDACTED]

[REDACTED]

[REDACTED]. Advertisements may also be posted in [REDACTED]

[REDACTED]

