## 13. STATISTICS

### 13.1. Description

Data stored in relational databases will be imported into SPSS software for statistical purposes. Statistical analysis will initially be reported in Excel. Data will be investigated for quality using range checks and frequency distribution. Underlying distributions of variables will be tested. Details of statistical analysis are described in Section 13.1.3.

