#### 13.1.1. Number of Participants

38 participants will be required to complete the study.

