#### 13.1.2. Significance

A p-value less than or equal to 5% will be considered to be statistically significant.

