#### 13.1.3. Analysis

Participants who complete the study treatment will be included in the analysis dataset. Reasons and frequency distribution of participants discontinued will be reported.

Data will be summarised as means  $\pm$  standard deviations for variables measured on an interval scale and median  $\pm$  inter-quartile range for ordinal variables. Statistical tests will be employed to determine significant differences in tear parameters, subjective symptoms and other parameters between Optime! Manuka+ Eye Drops and Systane Ultra eye drops. Normality will be assessed using the Shapiro-Wilk test. Independent t-tests will be used for comparison of continuous normally distributed data between the test and control groups. Non-parametric data will be analysed using Mann-Whitney U test. Proportions will be compared using  $\chi^2$  tests and associations will be examined using Pearson's correlation. The level of significance is set at  $\alpha=0.05$ . Statistical analysis will be performed using SPSS software V.22.0. The difference between the 28 days and baseline data will be used to quantify the treatment effect.

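### Section 13.3 lets the between-group test result decide whether outliers stay in, and never defines an outlier, so the 5% significance level is not assured

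*Combined protocol and SAP*

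**What the plan says.** Section 13.3 sets the inclusion rule: "Inclusion of outliers in the analysis will be based on the magnitude of change in test statistic with and without the outliers". Its next sentence gives the default: "Outliers will preferably be retained unless there is significant change in test results".

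The tests concerned are those of Section 13.1.3. For normal data, "Independent t-tests will be used for comparison of continuous normally distributed data between the test and control groups"; otherwise the Mann-Whitney U test applies, with Shapiro-Wilk deciding between the two. The quantity compared is the change score: "The difference between the 28 days and baseline data will be used to quantify the treatment effect". Section 13.1.2 sets the threshold: "A p-value less than or equal to 5% will be considered to be statistically significant".

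On data checks, Section 13.1 says "Data will be investigated for quality using range checks and frequency distribution" and adds that distributions will be tested. Neither statement supplies an outlier cut-off. Section 6.1.2 keeps the investigator unaware of the randomisation schedule. No section describes a data lock, a code break or masking of the analyst.

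**The concern.** The criterion for removing a value is its effect on the between-group result, not evidence of a faulty measurement. To apply the rule, someone must compute the treatment comparison with and without the suspect values and then choose the data set. Five things are left open: what counts as an outlier, how large a change is significant, whether flagging is per arm or pooled, whether exclusion can go in one direction only, and whether the decision is made blind.

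Section 13.3 exempts no outcome, so the rule reaches the primary endpoint in Section 6.2. With about 19 people per arm, one or two extreme change scores can decide the verdict. In that situation a reader could not take p ≤ 0.05 as a 5%-level result. Because the plan does not require the all-data analysis to be reported, the reader might never see the alternative.

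**Working it through.** **Inputs from the documents.** Alpha is 0.05 (13.1.2). The tests and the Shapiro-Wilk step come from 13.1.3. For completers, "38 participants will be required to complete the study" (13.1.1); enrolment is consistent with this, since 38 / (1 − 0.20) = 47.5, rounded up to 48. Section 6.1.3 instead says "A total of 46 participants with dry eye disease will be required to complete the study", so 46 was checked as well.

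**Assumptions.** Allocation is 1:1 (no ratio is stated), giving 19 per arm, with two-sided tests. The outlier cut-offs, the readings of a significant change, and the data distributions are all assumed, because the plan gives none.

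**Step 1: the nominal level.** With all values kept, the pooled t-test on normal data (19 v 19; 200,000 null trials; SE = √(0.05 × 0.95 / 200,000) ≈ 0.0005) rejected in 5.02%. The plan's 5% is reproduced.

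**Step 2: what the retention preference does.** Suppose a significant change means that the verdict crosses p = 0.05. If the verdicts with and without outliers agree, either may be reported. If they differ, the outliers go and the verdict without them is reported. Either way, the reported verdict is the one without outliers. This is a matter of logic: under this reading the stated preference for retention never affects significance.

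**Step 3: error rate, t-test only, normal data (%).** Same 200,000 null trials.

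| Flagging | Verdict crosses 0.05 | Change in t > 0.5 | Change in t > 1 | Drop only if significance is gained |
|---|---|---|---|---|
| Per arm, 1.5 IQR | 8.3 | 8.2 | 6.7 | 8.9 |
| Per arm, 2 SD | 9.8 | 9.2 | 7.2 | 10.6 |
| Per arm, 2.5 SD | 6.2 | 6.4 | 5.2 | 6.5 |
| Per arm, 3 SD | 5.2 | 5.2 | 5.1 | 5.2 |
| Pooled, 1.5 IQR | 5.0 | 5.4 | 5.2 | 5.9 |
| Pooled, 2 SD | 5.0 | 5.3 | 5.7 | 7.3 |

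For lognormal data (sigma 0.5), per-arm 1.5 IQR gave 12.2% (verdict crosses) and 12.9% (gain only).

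**Step 4: with the plan's Shapiro-Wilk step, re-applied after exclusion.** 10,000 null trials per distribution, SE 0.2 to 0.3 points. The change score is the difference of two lognormals (sigma 0.5, log-scale correlation 0.5). Figures in %, verdict-crossing reading:

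| | Normal | t, 4 df | Change score | Raw lognormal |
|---|---|---|---|---|
| All values kept | 4.9 | 5.2 | 4.8 | 5.2 |
| Per arm, 1.5 IQR | 7.8 | 9.3 | 9.0 | 11.4 |
| Per arm, 2 SD | 9.4 | 8.6 | 8.6 | 9.2 |

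Across the four distributions, per-arm 3 IQR or 3 SD gave 4.9 to 6.9%. All pooled cut-offs (1.5 or 3 IQR, 2 or 3 SD) gave 4.7 to 5.2%.

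If values are dropped only when that yields significance:
- pooled 3 IQR or 3 SD: 4.9 to 6.1%;
- pooled 1.5 IQR or 2 SD: 5.6 to 7.8%;
- per-arm 3 IQR or 3 SD: 4.9 to 7.2%;
- per-arm 1.5 IQR or 2 SD: 8.3 to 11.9%.

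**Step 5: two separate mechanisms.** Trimming each arm around its own centre shrinks the within-arm spread and understates the standard error; that alone inflates the error rate. Pooled flagging ignores arm, so under no effect the arm labels stay exchangeable and a symmetric rule holds close to 5%. Choosing after seeing the result is a second source. In Step 3 at 2 SD it adds 7.3 − 5.0 = 2.3 points pooled and 10.6 − 9.8 = 0.8 per arm. Across the Step 4 grid it adds up to 2.7 points pooled and 1.4 per arm.

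**Step 6: 46 completers (23 per arm; 4,000 trials, SE 0.3 to 0.5 points).** All kept: 5.0 to 5.2%. Verdict-crossing: pooled 4.9 to 5.4%, per-arm 1.5 IQR or 2 SD 8.0 to 11.4%. Gain only: pooled 5.1 to 7.4%, per-arm 1.5 IQR or 2 SD 8.5 to 11.9%. The pattern is the same.

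**The case against.** The strongest reply is that most of the inflation comes from assumptions the plan never makes. It nowhere mentions per-arm deletion at 1.5 IQR or 2 SD. With pooled flagging and a symmetric rule the rate stays near 5%. The one-directional reading is an inference from silence, since the wording of 13.3 is neutral as to direction and leans towards retention. The upper end also comes from raw lognormal data, whereas the plan analyses change scores. Finally, the rule matters only when outliers exist and their removal alters the test.

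Much of this is right about size. Dependence on the result is not the main driver in every reading, and some permitted readings are harmless. For change scores, shorter repeat runs (2,500 trials per distribution) put the worst case at about 10% to 11%, slightly below the overall top.

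It does not answer the point itself. The plan does not choose a harmless reading, and the choice stays open until results are visible. The preference for retention gives no protection under the verdict-crossing reading (Step 2). The Shapiro-Wilk switch to a rank test does not remove the inflation (Step 4).

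**Conclusion.** The concern holds. Section 13.3 makes inclusion depend on the between-group result and leaves the governing terms undefined, so the 5% level is not assured for the primary comparison or for any other between-group test.

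The documents do not fix a rate. With 19 per arm, 1:1 allocation and the plan's test selection, the false-positive rate runs from about 5% to about 12% over the readings and distributions tried. The low end is pooled flagging with a symmetric rule, or a wide cut-off on normal data. The high end is tight per-arm cut-offs. Confidence is high on the dependence on the result and on the missing definitions, but not on any one rate. The rule should be changed before any comparison by arm is run, because it cannot be credibly repaired afterwards.

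**What to change.** Replace the last two sentences of Section 13.3 with:

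> All recorded values are included in the primary analysis. A value is corrected or excluded only for a documented measurement or recording error, decided before the analyst has access to treatment allocation and without reference to any test result. An analysis excluding values more than 3 IQR outside the quartiles of the pooled (both arms combined) change scores is reported as a sensitivity analysis only.

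The 3 IQR cut-off is one workable choice. What matters is that it is fixed in advance and ignores treatment arm.

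The cost is two sentences, one short sensitivity analysis, and one added step: value checks must be recorded before the analyst sees allocation, which the plan does not currently provide for. The downside is that genuine extreme values stay in and may reduce precision a little. At an assumed true difference of 0.935 SD (not a figure from the documents; 2,000 trials, 19 per arm), power with all values kept versus pooled 3 IQR exclusion was 79.4 v 79.4% (normal), 87.6 v 87.7% (t with 4 df) and 85.8 v 85.3% (change score). The largest loss from excluding nothing was therefore 87.7 − 87.6 = 0.1 points.

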## **14. DATA HANDLING AND RECORD KEEPING**

### **14.1. Source Data**

The Investigator/Institution is to maintain the trial documents as specified in ICH GCP guidelines and as required by the applicable local regulations. The Investigator/Institution is to also take measures to prevent accidental or premature destruction of clinical trial-related documentation.

Paper Case Report Forms will be utilized for this clinical trial, and will be entered into Excel spreadsheets for importing into statistical software. For tests conducted that produce printed results, these should be included in the participant's file. Source data includes, but is not limited to printouts, diagrams, videos, photos, and any other paper, electronic or digital data that is the first recording of that information, and these must be maintained by the Investigator in the source files for the participant, or if unable to file (e.g. digital images), then reference should be made to their location. The clinic records will maintain a record of trial participation but will not be considered as the source.

### **14.2. Direct Access to Source Data/Documents**

The Investigator will conduct this clinical trial under HREC review. As necessary the Investigator will provide the HREC and appropriate regulatory authorities direct access to source data/documents for review.

### **14.3. Data Management**

The data will be accessible to study personnel only, secured and backed up regularly.

### **14.4. Data Archiving**

Electronic data will be stored in a secure off-site storage facility. Paper records are archived approximately 3 months after study closeout. The records are initially kept on site in a secure location, and may later be transferred to a secure off-site storage facility.

### **14.5. Retention of Essential Documents**

The Investigator/Institution is to retain essential documents until at least 2 years after the last approval of a marketing application in an ICH region and until there are no pending or contemplated marketing applications in an ICH region. However, these documents should be retained for longer if required by local regulatory agencies.

The Investigator/Institution must also retain essential documents for 15 years as per TGA requirements following the completion of a clinical trial. However, essential documents may need to be retained longer after consideration of the following: product liability and the potential need to produce records at any time during, and possibly beyond, the life of a product in the event of a claim as a result of an adverse outcome associated with the use of the product.

## **15. QUALITY CONTROL AND QUALITY ASSURANCE**

### **15.1. Ethical Considerations**

This trial requires HREC approval prior to start.

The Investigator is to ensure that the protocol, Participant Information Statement and Consent Form, available safety information, information about payment and compensation to participants, advertising or any clinical trial specific information provided to participants (including potential participants), the Investigator's CV and/or evidence of appropriate qualifications and any other documentation they may request are submitted, reviewed and approved. Any subsequent amendments will be reviewed and approved by an HREC prior to implementation.

The HREC must be appropriately constituted, and will perform its functions in accordance with the applicable local regulatory requirements (TGA and NHMRC) and GCP.

This trial will be conducted in accordance with local guidelines and requirements (including those of the NHMRC and TGA, as applicable).

#### **15.1.1. Confidentiality**

Confidentiality will be maintained throughout the clinical trial by all parties involved in accordance with guidelines under section 95 of the Privacy Act 1998, and guidelines approved under section 95a of the Privacy Act 1998 (December 2001). Data will be secured against unauthorised access.

Privacy and confidentiality of information about each clinical trial participant will be preserved in the reports and any publication of the clinical investigation data.

#### **15.1.2. Informed Consent**

The nature and purpose of the trial will be fully explained to each participant. Written informed consent must be obtained from each participant prior to any trial procedures being performed.

The informed consent documentation to be used for the trial will include all the elements of informed consent per GCP, and TGA requirements as applicable, and will be reviewed and approved by the HREC prior to use.

#### **15.1.3. Protocol Amendments**

The Investigator will review deviations to determine the need to amend the protocol or to terminate the investigation. Justification for any changes will be provided.

Protocol amendments will be submitted to the HREC for review and approval prior to implementation, unless the change required is to eliminate an immediate hazard to trial participants, or involves only administrative and/or logistical aspects of the trial (e.g. Change in contact numbers).

#### **15.1.4. Investigator Responsibilities**

The Investigator is responsible for ensuring participant safety and data quality by: protocol compliance, adherence to GCP and local regulatory requirements, and the Declaration of Helsinki. The Investigator should be appropriately qualified and legally entitled to practice, and be trained in the proper method of obtaining informed consent.

The Investigator must have the appropriate resources to conduct the clinical trial, be familiar with the protocol and agree to adhere to it, support monitoring and auditing activities, make the necessary arrangements to ensure proper conduct and completion of the clinical trial, and ensure the protection and welfare of the participant, including arranging any emergency treatment as needed.

The Investigator must ensure written HREC approval is received prior to the start of the clinical trial, that the HREC is kept informed of the clinical trial progress, including serious/adverse events and deviations as required by them, and that any changes to the protocol are notified to the HREC and receive written approval prior to implementation.

The Investigator must try to ensure adequate participant recruitment; that all necessary and appropriate information is given to potential participants to ensure informed consent; to ensure informed consent is taken and documented; and that clinical records indicate the participant is enrolled in a clinical trial. The Investigator must ensure that clinical trial participants are provided with emergency contact details along with a procedure to follow in the case of an emergency, and that clinical trial participants are kept informed as pertinent new information becomes available that may affect their decision to participate.

The Investigator has primary responsibility for the accuracy, legibility and security of all clinical investigation data, documents and participant records at the investigator site during and after the clinical trial. Case Report Forms are to be signed by the Investigator, and any alterations to data are to be by authorised personnel, initialled and dated by same.

The Investigator must ensure that data be kept for the minimum time as specified by this protocol, investigational product must be accounted for (the quantity received must be reconciled with the quantities used, discarded or returned), and must also be responsible for the supervision and assignment of duties to all responsible for the conduct and evaluation of the clinical trial for the investigator centre involved.

## **16. FINANCING AND INSURANCE**

Memorandum of Agreement can be provided on request.

## **17. PUBLICATION POLICY**

Please refer to Memorandum of Agreement.

---

**APPENDIX I**

**DECLARATION OF HELSINKI**

---

## APPENDIX I: WORLD MEDICAL ASSOCIATION DECLARATION OF HELSINKI

---

### Ethical Principles for Medical Research Involving Human Subjects

The Declaration of Helsinki (Document 17.C) is an official policy document of the World Medical Association (WMA), the global representative body for physicians.

Adopted by the 18th WMA General Assembly, Helsinki, Finland, June 1964 and amended by the  
29th WMA General Assembly, Tokyo, Japan, October 1975  
35th WMA General Assembly, Venice, Italy, October 1983  
41st WMA General Assembly, Hong Kong, September 1989  
48th WMA General Assembly, Somerset West, Republic of South Africa, October 1996 and the  
52nd WMA General Assembly, Edinburgh, Scotland, October 2000

#### A. INTRODUCTION

1. The World Medical Association has developed the Declaration of Helsinki as a statement of ethical principles to provide guidance to physicians and other participants in medical research involving human subjects. Medical research involving human subjects includes research on identifiable human material or identifiable data.
2. It is the duty of the physician to promote and safeguard the health of the people. The physician's knowledge and conscience are dedicated to the fulfilment of this duty.
3. The Declaration of Geneva of the World Medical Association binds the physician with the words, "The health of my patient will be my first consideration," and the International Code of Medical Ethics declares that, "A physician shall act only in the patient's interest when providing medical care which might have the effect of weakening the physical and mental condition of the patient."
4. Medical progress is based on research which ultimately must rest in part on experimentation involving human subjects.
5. In medical research on human subjects, considerations related to the well-being of the human subject should take precedence over the interests of science and society.
6. The primary purpose of medical research involving human subjects is to improve prophylactic, diagnostic and therapeutic procedures and the understanding of the aetiology and pathogenesis of disease. Even the best proven prophylactic, diagnostic, and therapeutic methods must continuously be challenged through research for their effectiveness, efficiency, accessibility and quality.
7. In current medical practice and in medical research, most prophylactic, diagnostic and therapeutic procedures involve risks and burdens.
8. Medical research is subject to ethical standards that promote respect for all human beings and protect their health and rights. Some research populations are vulnerable and need special protection. The particular needs of the economically and medically disadvantaged must be recognized. Special attention is also required for those who cannot give or refuse consent for themselves, for those who may be subject to giving consent under duress, for those who will not benefit personally from the research and for those for whom the research is combined with care.
9. Research Investigators should be aware of the ethical, legal and regulatory requirements for research on human subjects in their own countries as well as applicable international requirements. No national ethical, legal or regulatory requirement should be allowed to reduce or eliminate any of the protections for human subjects set forth in this Declaration.

#### B. BASIC PRINCIPLES FOR ALL MEDICAL RESEARCH

10. It is the duty of the physician in medical research to protect the life, health, privacy, and dignity of the human subject.
11. Medical research involving human subjects must conform to generally accepted scientific principles, be based on a thorough knowledge of the scientific literature, other relevant sources of information, and on adequate laboratory and, where appropriate, animal experimentation.
12. Appropriate caution must be exercised in the conduct of research which may affect the environment, and the welfare of animals used for research must be respected.
13. The design and performance of each experimental procedure involving human subjects should be clearly formulated in an experimental protocol. This protocol should be submitted for consideration, comment, guidance, and where appropriate, approval to a specially appointed ethical review committee, which must be independent of the investigator, the sponsor or any other kind of undue influence. This independent committee should be in conformity with the laws and regulations of the country in which the research experiment is performed. The committee has the right to monitor ongoing trials. The researcher has the obligation to provide monitoring information to the committee, especially any serious adverse events. The researcher should also submit to the committee, for review, information regarding funding, sponsors, institutional affiliations, other potential conflicts of interest and incentives for subjects.

---

